9.2 Methods and Timing for Assessing and Recording Safety Parameters

9.2.1 Adverse Events

An AE is defined as any untoward medical occurrence in a patient or clinical investigation participant administered a pharmaceutical product, which does not necessarily have a causal relationship with this treatment. An AE can therefore be any unfavorable and unintended sign (including an abnormal laboratory finding), symptom, or disease temporally associated with the use of a medicinal product,

whether or not considered related to the medicinal product. Information to be collected on AEs includes event description, time of onset, clinician's assessment of severity, relationship to study product, and time of resolution/stabilization of the event. AE assessment should be made only by those with the training and authority to make a diagnosis.

In this protocol, laboratory results are considered AEs when the result is Grade 2 or above.

Any medical condition that was present at the time that the subject was enrolled should not be reported as an AE, but should be reported as a pre-existing condition on the Medical History Form. However, if this condition occurs with greater frequency or severity during the study, it should be recorded as an AE.

AEs, including laboratory abnormalities that are Grade 2 and above, should always be assessed for severity and relationship to study products.

This study will collect and record solicited local and systemic reactogenicity and unsolicited AEs. For clarity, solicited reactogenicity refers to AEs specifically asked about during the 7-day post-vaccination period. Unsolicited events are those not specifically solicited, but may be reported by the subject at any time or observed by study staff while the subject is at a clinic for a study visit. If a new solicited event is reported by the subject outside of the 7-day post-vaccination window, this event will be recorded as an "unsolicited AE" because it will be outside of the 7-day window for collection of solicited reactogenicity.

SAEs are defined in Section 9.2.8.

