3.2.2 Safety Endpoints

The safety profile of IVACFLU-A/H5N1 will be evaluated by the proportion of subjects experiencing AEs, related or not related, of the following five categories for all subjects and by age group (18-40 years of age and 41-60 years age):

- Number and percentage of subjects with solicited local and systemic adverse events within 30 minutes after each vaccination.
- Number and percentages of subjects with solicited local adverse events (redness, swelling, pain, induration, and tenderness) over a 7-day period (Days 1-7; Days 22-28) post each vaccination.
- Number and percentages of subjects with solicited systemic/general adverse events (fever, fatigue/malaise, muscle aches (generalized), joint aches, chills, nausea, vomiting, and headache) over a 7-day period (Days 1-7; Days 22-28) post each vaccination.
- Number and percentages of subjects with unsolicited adverse events for 21 days post each vaccination.
- All serious adverse events (SAEs) occurring over the entire study period. (Days 1-91).

4 Study Design

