4. Blood specimens will be collected for immunological testing prior to vaccination. In Phase 2, blood specimens will be collected from all study participants (n=300). In Phase 3, blood specimens will be collected from approximately 300 subjects receiving the IVACFLU-A/H5N1 (vaccinees) among 500 enrolled at one of the three provinces, assuming equal enrollment.
5. Study product will be masked so that staff administering it and the subject are unaware of product allocation. The product will be administered and subjects will be carefully monitored for adverse reactions for 30 minutes after vaccination, with a completion of a 30-minute Reactogenicity Assessment.
6. During the first week (Days 1 to 7) following vaccination, subjects will be asked to record local and systemic signs and symptoms using preprinted Diary Cards, a thermometer, and a small ruler. Concomitant medications will also be recorded. In addition to solicited signs, subjects will be asked to report any other adverse events. Members of the investigator's clinical team will visit subjects on Day 2 and call them (or visit, if needed) on Day 6 to check that subjects are correctly completing the Diary Card, to check on the subjects' well-being, and remind the subject to return on Day 8. *Note: For contact with the subject, calling is an acceptable alternative to home visit.*
7. Subjects will return to the study clinic 7 days after injection of study product (on Day 8 +/- 2 days). At that time, the study staff will review the subjects' Diary Cards with them and transcribe all adverse events onto the case report forms. He or she will also do a targeted physical exam that focuses only on reported symptoms from the participant. For Phase 2 subjects only, blood specimens will be collected for clinical safety laboratory tests.
8. Two days before subjects are scheduled to receive Injection 2, subjects will be called to remind them of the next visit to the study clinic and to check on the subjects' well-being.

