7.3.3 Seventh Day after Injection 1 (Day 8 ± 2)

1. Study staff will confirm subject identity.
2. Study staff will review the subject Diary Card and interim history with the subject and inquire about any new medical events since medical histories were last updated. Any AEs that have occurred will be recorded in the appropriate section(s) of the CRF. Study staff will collect the Diary Card and keep it as a source document.
3. A study clinician will perform a targeted physical examination and record the information on the CRF. Results will be reviewed by study staff and discussed with the subject. Any AEs that have occurred will be recorded in the appropriate section(s) of the CRF.
4. **FOR PHASE 2 SUBJECTS ONLY:** If not done previously, the study clinician will review the results of the selected biochemical and hematological tests conducted from the blood drawn on S1 with the subject.
5. **FOR PHASE 2 SUBJECTS ONLY: Blood is collected for clinical safety laboratory testing** (ALT, creatinine, bilirubin, hemoglobin, and white cell and platelet counts). Specimen collection information must be documented on the CRF and in specimen collection forms.
6. The subject will be instructed that if the subject later experiences an AE requiring medical care, the subject should inform the investigator as soon as possible and seek medical care as appropriate. If the subject visits a health care provider, the subject should be sure to inform the health care provider of participation in this study and give the health care provider the contact information for the investigator.

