9.2.6 Solicited Local and Systemic Reactions

Specific local and systemic reactions will be solicited (specifically asked of subjects) while subjects are in the study. These specific reactions, which are signs and symptoms, will be graded by a study clinician using the Toxicity Table for Grading Adverse Events (see Toxicity Table in Appendix B). Grading will use predefined scales based on functional assessment or magnitude of reaction, where available. Where grading scales are not provided, the reaction will be graded for severity based on interference with subject functionally, as for all other AEs (see Section 9.2.1). Severity of redness, swelling, and induration at the injection site should always be graded based on size.

Local Reactions:

- Size of redness (at site of injection) in cm
- Size of swelling (at site of injection) in cm
- Size of induration (hardness at site of injection) in cm
- Pain (at site of injection)
- Tenderness (at site of injection)

Systemic Reactions:

- Fever/body temperature (and body location of measurement)
- Fatigue/malaise
- Generalized muscle aches
- Joint aches/pains
- Chills
- Nausea
- Vomiting
- Headache

Solicited Local and Systemic Reactogenicity will be collected through study Day 7. If a solicited sign or symptom has started during the 7 days post vaccination and continues beyond the 7 days, it will continue to be reported as a reactogenicity symptom. Any solicited sign or symptom starting after 7 days post vaccination will be recorded as an “unsolicited AE”.

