⁴ Newcombe, R. G. (1998), "Interval Estimation for the Difference Between Independent Proportions: Comparison of Eleven Methods," *Statistics in Medicine*, 17, 873–890.

separately by Day 22/Day 1, Day 43/Day1, and the HAI and MN tests. No comparisons will be made between the IVACFLU-A/H5N1 dose groups and the placebo group.

VIII. ANALYSIS OF SAFETY OBJECTIVES

The safety profile will be parameterized as the frequency and proportion of specific symptoms/problems in each group falling into one of the following five categories for all subjects and by age group (18-40 years of age and 41-60 years age).

- **Immediate reactions** (solicited local and systemic adverse events), occurring in the first 30 minutes post vaccination on Day 1 and Day 22, as observed by study staff. The reaction will include
 - Local signs/symptoms: redness, swelling, hardness, pain, or tenderness of the injected site of upper arms;
 - Systemic signs/symptoms: headache, fever, fatigue/malaise, muscle aches, joint aches, nausea, vomiting, and chills.
- **Solicited adverse local reactions** occur over a 7-day period (Days 1-7; Days 22-28) post each vaccination, identified or observed by study staff during home visits and/or reported by parent at any time through Day 7. Specifically, the following local signs and symptoms at site of injection will be assessed and documented as solicited adverse reactions:
 - Redness
 - Swelling
 - Induration
 - Pain
 - Tenderness
- **Solicited adverse systemic reactions** occur over a 7-day period (Days 1-7; Days 22-28) post each vaccination, identified or observed by study staff during home visits and/or reported by parent at any time through Day 7. Specifically, the following systemic reactions will be assessed and documented as solicited adverse reactions:
 - Fever/body temperature (and body location of measurement)
 - Fatigue/malaise
 - Generalized muscle aches
 - Joint aches/pains
 - Chills
 - Nausea
 - Vomiting
 - Headache Body temperature

If a solicited sign or symptom has started during the 7 days post vaccination and continues beyond the 7 days, it will continue to be reported as a reactogenicity symptom. Any solicited sign or symptom starting after 7 days post vaccination will be recorded as an “unsolicited AE”. Adverse Reactions will be graded (i.e., Grade 1 to 4) and subcategorized as those deemed related to vaccination or not by a study clinician.

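### Section 9.2.1 classifies a solicited sign by when it is reported, sections 9.2.6 and 9.2.7 and both SAPs by when it starts, and both SAPs add a report-time limit; one onset-based rule is needed.

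*Protocol*

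**What the plan says.** **Report-time rule.** Protocol 9.2.1 opens its rule with "If a new solicited event is reported by the subject outside of the 7-day post-vaccination window" and has such an event recorded as unsolicited. The reason given also concerns collection: "because it will be outside of the 7-day window for collection of solicited reactogenicity".

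**Start-time rule.** Protocol 9.2.6 says "Any solicited sign or symptom starting after 7 days post vaccination will be recorded as an" unsolicited AE. Section 9.2.7 and section VIII of both SAPs repeat this. The same paragraph of 9.2.6 also sets a collection limit: "Solicited Local and Systemic Reactogenicity will be collected through study Day 7".

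**SAP definitions.** In section VIII of both the interim and the final SAP, solicited local and systemic reactions are those "identified or observed by study staff during home visits and/or reported by parent at any time through Day 7". Each SAP therefore holds a report-time condition and a start-time rule.

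**Endpoint window and visits.** The solicited endpoints in 3.2.2 run "over a 7-day period (Days 1-7; Days 22-28) post each vaccination". The card is reviewed at visits on Day 8 ± 2 and Day 29 ± 2 (7.3.3, 7.3.7), where staff also ask about new medical events. Section 8.1.2 has a clinician evaluate the solicited signs on those days, with onset dates recorded.

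**Use of the class.** Solicited events are compared between groups by test; unsolicited events are not (protocol 12.4.2; section VIII of the final SAP; sections V and VIII of the interim SAP).

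**The concern.** Sections 9.2.1 and 9.2.6 are both recording instructions, and they use different dates. The planned card-review visit falls, on its nominal day, one day after the endpoint window closes. A subject who left a Day 5 reaction off the card and mentions it on Day 8 has a reaction inside the endpoint window and a report outside it. Two sites, or two staff members, could put the same event in different classes and both be following the protocol.

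At stake is whether that event counts in the solicited percentages and enters the vaccine-placebo comparison. The question arises mainly for subjects who keep the card poorly, so recorded reactogenicity would depend partly on diary discipline and on the day of the appointment.

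**Working it through.** The plan states no figure on this point, so the check applies each rule to the same event. Day 1 is the day of injection.

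**1. One event under each rule.** A listed sign starts on Day 5, is not on the card, is not told at the Day 2 or Day 6 contact, and is first mentioned at the Day 8 visit.

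| Place | What is tested | Result |
|---|---|---|
| Protocol 9.2.1, read literally | date of report | unsolicited |
| Protocol 9.2.6, 9.2.7 | date of start | solicited |
| Both SAPs VIII, start sentence | date of start | not moved to unsolicited |
| Both SAPs VIII, definition of solicited reactions | in the window and identified or reported through Day 7 | does not meet the definition |

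The protocol gives two answers, and neither SAP settles the matter.

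**2. All combinations of onset and visit day.** The visit window is Days 6 to 10. For a sign first told at the visit, onset can be any day up to the visit.

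- Visit on Day 6 or 7: 6 + 7 = 13 combinations. The two rules agree in all 13.
- Visit on Day 8, 9 or 10: 8 + 9 + 10 = 27 combinations. Onset on Days 1-7 gives unsolicited under 9.2.1 and solicited under 9.2.6, which is 3 × 7 = 21 conflicts.
- The other 27 − 21 = 6 have onset on Day 8 (3), Day 9 (2) or Day 10 (1). The 3 with onset on Day 9 or 10 are unsolicited under both rules. The 3 with onset on Day 8 are taken up in step 4.

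These are counts of cells and say nothing about how often such events occur. The same pattern holds 21 days later, with visits on Days 27 to 31 and onset on Days 22-28.

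**3. Direction.** A sign reported inside the window must have started inside it. The events that are solicited under 9.2.1 are therefore a subset of those solicited under 9.2.6. For a given denominator, following 9.2.1 leaves each solicited percentage unchanged or lowers it; it cannot raise it.

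**4. Onset on Day 8.** If the 7 days post vaccination are Days 1-7, as 3.2.2 has it, a Day 8 onset is unsolicited under the start rule. If they are counted as the visit schedule does, where Day 8 is 7 days after injection (4.6.3, 7.3.3), the start sentence first applies on Day 9. The text allows both counts. The boundary is also unsettled after Injection 2: 7.3.6 is headed Days 22-28 but has the card kept until D29.

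**The case against.** The strongest reply is that this is a narrow slip of wording. A daily diary entry is itself a report by the subject (7.3.2), so anything written on the card in the window was reported in time even if staff first read it on Day 8. Staff also contact subjects on Days 2 and 6, and 23 and 27. Section 9.2.1 speaks of a new event, which can be read as newly started, and sites may follow the sections devoted to these categories, 9.2.6 and 9.2.7. All of this stands and limits the scope. The two instructions still differ as written.

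Four stronger readings are tempting, and the documents do not support them:

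- *Every reaction that staff first learn of at the Day 8 or Day 29 visit is affected.* Diary entries and the interim contacts remove most of the ground for this, and a visit on Day 6 or 7 produces no conflict.
- *A Day 8 onset falls in no category.* This needs the elapsed-day count. The endpoint text and the collection limit in 9.2.6 point to Days 1-7, and unsolicited AEs are defined in 9.2.7 and both SAPs as those that are not solicited, which can absorb a Day 8 onset.
- *The loss can be sized by scaling the Phase 1 rate of 81.3% (26/32 at 15 mcg) by an assumed share of late reporters.* That rate is for subjects with at least one solicited event over both vaccinations, so a subject leaves it only if no solicited reaction at all was recorded in the window. It also includes cough and sore throat, which are not solicited here. Both SAPs exclude from the solicited analysis a subject whose card was not completed, so the denominator would not stay fixed either. No share of late reporters is given.
- *Automatic relatedness is lost as well.* Section 9.2.3 ties it to reactogenicity that occurs in the 7-day period, whatever the date of report.

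**Conclusion.** The inconsistency is real, and 9.2.1 should be corrected. Read literally, it takes a true 7-day reaction out of the solicited endpoint and out of the tested comparison solely because it was mentioned late. The SAPs do not resolve this, because each combines a start rule with a report-time limit.

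The affected group is confined to signs that started in the window, were absent from the card and from both contacts, and were first told at a visit after the window. Its size cannot be computed from the documents. The direction, no change or a lower solicited percentage, rests on two assumptions: that sites follow the literal wording of 9.2.1, and that the denominator is the same under both rules. A reader might infer that the solicited rates are biased downwards as a matter of fact; the documents show only that they would be if 9.2.1 were the rule applied. The boundary at Day 8 is an ambiguity to be removed by naming the days.

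**What to change.** Adopt one rule everywhere: a listed sign is classified by its onset, counted from the actual injection with the injection day as Day 1. Onset on Days 1-7 after Injection 1, and on the same count after Injection 2, is solicited whenever and however it is reported. Later onset is unsolicited.

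- **Protocol 9.2.1:** make the condition that the event starts outside the window, in place of its being reported outside it.
- **Protocol 9.2.6, 9.2.7 and section VIII of both SAPs:** replace the phrase about 7 days post vaccination with the study days.
- **Section VIII of both SAPs:** delete the clause that limits solicited reactions to those reported by a parent through Day 7, for local and for systemic reactions. The reference to a parent does not fit a trial in adults in any case.
- **Protocol 7.3.6:** reconcile the diary period, which runs to D29, with the Days 22-28 endpoint.

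The cost is wording alone. Onset is already collected (8.1.2, 9.2.1), so no new data are needed, and events already recorded can be classified from their onset dates. The one downside is that a few events move from the unsolicited to the solicited table.

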9.2.2 Severity of Event

All AEs, including clinical laboratory test results Grade 2 and above, will be assessed by a study clinician to quantify severity using a protocol-defined grading system. This study will use the Toxicity Table for Grading Adverse Events (see Toxicity Table in appendix). For events not included on the table, the following guidelines will be used to quantify intensity:

Grade	Description for grading when an event is not on Toxicity Table
1 (Mild)	Events require minimal or no treatment and did not interfere with the subject's daily activities.
2 (Moderate)	Events resulted in a low level of inconvenience or concern to the subject with therapeutic methods. Moderate events might cause some interference with functioning.
3 (Severe)	Events interrupt the subject's functioning and might require systemic drug therapy or other treatment. Severe events are usually incapacitating.
4 (Life threatening)	Any adverse experience that places the subject, in the view of the investigator, at immediate risk of death as it occurred (The investigator should not grade a reaction as life-threatening that had it occurred in a more severe form, might have caused death).
Basic Self-Care Functions – Adult: Activities such as bathing, dressing, toileting, transfer/movement, continence, and feeding.	

Usual Social & Functional Activities – Adult: Adaptive tasks and desirable activities, such as going to work, shopping, cooking, use of transportation, pursuing a hobby, etc.

Changes in Severity of an Event

Changes in the severity of an AE should be documented to allow an assessment of the duration of the event at each level of intensity to be performed. AEs characterized as intermittent require documentation of onset and duration of each episode.

9.2.3 Relationship to Study Vaccines

The clinician's assessment of an AE's relationship to study product is part of the documentation process. The clinician must determine whether there is a reasonable possibility that the investigational product(s) caused or contributed to an AE. It is essential to have the best assessment possible as to whether adverse events are related to investigational products.

The relationship assessment, based on clinical judgment, should rely on the following:

- Temporal (time-based) relationship between the event and administration of the investigational product.
- Plausible biological mechanism for the investigational product to cause the AE.
- Possible alternative etiology for the AE.
- Previous reports of similar AEs associated with the investigational product or other vaccines in the same class.

To help assess, the following guidelines will be used:

Related – There is a reasonable possibility that the study vaccine caused the AE. “Reasonable possibility” means that there is evidence to suggest a causal relationship between the study product and the AE.

Not Related – There is not a reasonable possibility that the administration of the study product caused the event.

Any solicited local or systemic reactogenicity that occurs during the 7-day period post-injection is automatically regarded as related.

9.2.4 Guidelines for AEs

To improve the quality and precision of acquired AE data, the PI should observe the following guidelines:

- Whenever possible, use recognized medical terms when recording AEs on the AE CRF. Do not use colloquialisms and/or abbreviations.
- If known, record the diagnosis (i.e., disease or syndrome) rather than component signs, symptoms, and laboratory values on the AE CRF (e.g., record congestive heart failure rather than

dyspnea, rales, and cyanosis). However, signs and symptoms that are considered unrelated to an encountered syndrome or disease should be recorded as individual AEs on the CRF (e.g., if congestive heart failure and severe headache are observed at the same time, each event should be recorded as an individual AE).

- AEs occurring secondary to other events (e.g., sequelae) should be identified by the primary cause. A “primary” AE, if clearly identifiable, generally represents the most accurate clinical term to record on the AE CRF. If a primary serious AE (SAE) is recorded on an SAE CRF, events occurring secondary to the primary event should be described in the narrative description of the case.

For example:

Orthostatic hypotension → Fainting and fall to floor → Head trauma → Neck pain

The primary AE is orthostatic hypotension.

- Out of range laboratory results that are Grade 2 or higher will be considered AEs and should be entered onto an AE form.
- Death is an outcome of an event. The event that resulted in the death should be recorded and reported on the SAE CRF.
- For hospitalizations related to surgical or diagnostic procedures, the illness leading to the surgical or diagnostic procedure should be recorded as the SAE rather than the procedure itself. The procedure should be recorded in the case narrative as part of the action taken in response to the illness.
- Pregnancies are not considered AEs. They will be recorded on a separate Pregnancy CRF. Pregnancy outcomes that include stillbirth and any congenital anomalies must be reported as SAEs.

